3.2.3 Arm C: Avelumab + Utomilumab (4-1BB) + PF-04518600 (OX40)

As of Amendment Version 05, in Arm C of avelumab, utomilumab (4-1BB), and PF-04518600 (OX40), there will be no dose escalation. The escalation of PF-04518600 (OX40) in combination with fixed doses of avelumab and utomilumab (4-1BB) was performed under a previously conducted Pfizer protocol.

The Arm C MTD expansion will enroll up to 14 patients at the established safe dose for additional safety and correlative studies to establish the RP2D for this combination.

PF-04518600 (OX40) will be administered at the fixed dose of 0.3 mg/kg by IV on Days 1 and 15 of each 28-day cycle or every 2 weeks. Utomilumab (4-1BB) will be administered at the fixed flat dose of 20 mg IV on Day 1 of each 28-day cycle or every 4 weeks. Avelumab will be administered at the fixed dose of 10 mg/kg IV on Day 15 of

Cycle 1 and Days 1 and 15 of subsequent cycles. Premedications will be administered per institutional standard.

On days when avelumab, utomilumab, and PF-04518600 are administered, avelumab will be administered first followed by utomilumab then PF-04518600.

Patients will be restaged at the end of every two cycles and tumor response evaluation will be based on RECIST 1.1 and irRECIST. Patients may be allowed to continue treatment after two cycles of avelumab combinations if there is continued clinical response or disease stabilization and patients do not have significant toxicities. A patient may continue treatment on this combination therapy until the patient experiences confirmed disease progression, unacceptable adverse event(s), intercurrent illness that prevents further administration of treatment, and/or treatment is discontinued following investigator's decision to withdraw the patient, pregnancy, patient withdraws consent, noncompliance with trial treatment or procedure requirements, or administrative reasons.

Table 5: Dosing for Arm C: Avelumab + Utomilumab (4-1BB) + PF-04518600 (OX40)

Dose Level	PF-04518600 (OX40) IV Every 2 Weeks Starting Cycle 1 Day 1	Utomilumab (4-1BB) IV Every 4 Weeks Starting Cycle 1 Day 1	Avelumab IV Every 2 Weeks Starting Cycle 1 Day 15
MTD/RP2D Determined by Pfizer	0.3 mg/kg	20 mg	10 mg/kg

As of Amendment Version 06, the avelumab dosing for Arm C was revised; therefore, a new cohort of 14 patients was enrolled.

3.2.4 Arm D: Avelumab + Utomilumab (4-1BB) + Radiation

In the dose escalation phase, the dose of radiation will be de-escalated in combination with fixed doses of utomilumab (4-1BB) and avelumab to evaluate the safety, tolerability, and MTD in patients with advanced solid tumors.

Once the MTD or RP2D is determined, the Arm D MTD expansion will enroll up to 14 patients at the previously established safe dose for additional safety and correlative studies to establish the RP2D for this combination.

Radiation will be administered to 1-3 metastatic sites. This will be de-escalated from a total of 24 Gy to 21 Gy. The technique will be stereotactic radiation via intensity-modulated radiation therapy (IMRT) or Volumetric modulated arc therapy (VMAT). The radiation lead-in will occur within Days -5 to -1 with a +/- 3 day window. There will be 3 fractions or days of radiation. In all cases, the radiation must initiate and end within the radiation lead-time. Cycle 1 Day 1 study drug treatment should begin within 3 days of last dose of radiation.

Utomilumab (4-1BB) will be administered at the fixed flat dose of 100 mg IV on Day 1 of each 28-day cycle or every 4 weeks. Avelumab will be administered at the fixed dose of 10 mg/kg IV on Day 15 of Cycle 1 and Days 1 and 15 of each subsequent 28-day cycle or every 2 weeks. Premedications will be administered per institutional standard.

On days when both avelumab and utomilumab are administered, avelumab will be administered first.

Patients will be restaged at the end of every two cycles and tumor response evaluation will be based on RECIST 1.1 and irRECIST. Patients may be allowed to continue treatment after two cycles of avelumab combinations if there is continued clinical response or disease stabilization and patients do not have significant toxicities. Following radiation, a patient may continue treatment on this combination therapy until the patient experiences confirmed disease progression, unacceptable adverse event(s), intercurrent illness that prevents further administration of treatment, and/or treatment is discontinued following investigator's decision to withdraw the patient, pregnancy, patient withdraws consent, noncompliance with trial treatment or procedure requirements, or administrative reasons.

Table 6: Dosing for Arm D: Avelumab + Utomilumab (4-1BB) + Radiation

Dose Level	Radiation Days -5 to -1	Utomilumab (4-1BB) IV Every 4 Weeks Starting Cycle 1 Day 1	Avelumab IV Every 2 Weeks Starting Cycle 1 Day 15
1 (Start)	24 Gy in 8 Gy / fraction for 3 fractions	100 mg	10 mg/kg
-1	21 Gy in 7 Gy/ fraction for 3 fractions	100 mg	10 mg/kg

As of Amendment Version 09, the avelumab and radiation dosing for Arm D was revised; therefore, the dose de-escalation was re-started.

3.3 Dose-Limiting Toxicity (DLT) Definition

Severity of adverse events will be graded according to CTCAE version 4.03. For the purpose of dose de-escalation, a DLT is defined as any of the following adverse events occurring in the first 56 days following Cycle 1 Day 1 (dosing of PF-04518600 (OX40) and/ or Utomilumab (4-1BB)) of study participation during the dose de-escalation, unless there is a clear alternative explanation (eg, related to underlying disease/ progression):

- Discontinuation of a patient due a toxicity that is at least possibly study drug(s) and/or radiation related before completing DLT period.
- Delay by more than 4 weeks (28 days) in receiving the next scheduled cycle due to persisting toxicities attributable to the study drug(s) and/or radiation.
- Non Hematologic (all will be graded according to CTCAEv4.03 criteria):
 - Grade \geq 3 nausea/vomiting or diarrhea lasting \geq 72 hours while taking optimal supportive medications;
 - Grade \geq 3 fatigue lasting \geq 7 days;
 - Grade \geq 2 pneumonitis lasting \geq 7 days despite treatment with corticosteroids;
 - Grade \geq 3 rash lasting \geq 7 days despite treatment;
 - Grade \geq 3 immune related toxicities lasting \geq 7 days despite treatment with corticosteroids;

- Any other Grade ≥ 3 non-hematological toxicity (except for electrolytes abnormalities that are reversible and asymptomatic or hair loss which is not dose-limiting);
- Grade ≥ 3 AST, ALT, or total bilirubin elevation lasting ≥ 7 days.
- Hematologic:
 - Grade 4 neutropenia [absolute neutrophil count (ANC) $< 500/\text{mm}^3$] lasting ≥ 7 days;
 - Febrile neutropenia (ANC $< 1000/\text{mm}^3$ with a single temperature $\geq 38.3^\circ\text{C}$ or sustained temperature of $> 38^\circ\text{C}$ for over 1 hour);
 - Grade ≥ 3 thrombocytopenia associated with bleeding, or grade 4 thrombocytopenia;
 - Grade 4 anemia.

Elevation of amylase and/or lipase without clinical and/or radiographic evidence of pancreatitis are not considered DLT, and the patient can resume treatment at any grade at the discretion of the treating physician in consultation with the PI.

During the dose de-escalation portion (Arm D) of the study, patients who missed any doses during the DLT period for reasons unrelated to study drug are not evaluable for DLT and will be replaced.

For both de-escalation (up to 4 cycles) and expansion (up to 6 cycles) phases of the study, if a patient comes off study unrelated to toxicity or progression of disease (such as intercurrent disease or social reasons), the patient for that cohort will be replaced.

The expansion cohort for each arm will be stopped early if the aggregate DLT rate $> 33\%$ for that particular arm. The aggregate DLT rate for each arm will include patients that were treated at the same dose level in the dose escalation or de-escalation phase.

In rare instances, an event may fall within the definition of a DLT as defined above but the event may be considered not a DLT (eg: not clinically meaningful/significant). If this occurs, the PI will thoroughly review the event and supporting data and the reasons for not considering the event a DLT will be clearly documented with supporting

rationale. In addition, other events may occur which do not meet the definition of a DLT but are concerning to the PI, may be then considered to be DLTs.

In the event that a DLT is at least possibly related to the study drug(s) occurs, patients will halt treatment with the combination until symptoms resolve to the grade outlined in [Section 5.2.4](#). Study drug(s) may be restarted as described in [Section 5.2.4](#).

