3.4 Maximum Tolerated Dose (MTD) Definition

In the Dose De-Escalation cohorts, patients will be assigned sequentially into cohorts of up to six patients in each cohort. Three to six patients will initially be enrolled in each cohort for DLT observation. A total of six patients will be enrolled in a cohort in the event that a DLT is observed in one of the first three patients and/or additional safety data are needed.

The MTD is defined as the highest dose level with less than 2 patients with DLT out of at least six patients in the cohort. Management and dose modifications associated with adverse events are outlined in subsequent protocol sections.

For all Arms, the DLT assessment window is 56 days (from Cycle 1 Day 1). In the absence of DLTs, patients continue consecutive treatment. For patients who experience a DLT, they may continue treatment with modifications if the toxicity resolves and at discretion of the attending physician and PI. In the absence of clinical deterioration and if the investigator believes that the patient continues to receive benefit from the treatment, patients may continue to receive study drug combinations after the first indication of progressive disease until a confirmation scan is obtained.

To understand and safeguard against potential cumulative toxicities the study team will continue to monitor the occurrence of study drug related SAEs and AEs throughout the treatment period and during potential treatment extensions to allow for dose correction in the event of cumulative immune-mediated toxicities.

Delayed onset of significant toxicity at the discretion of the investigator will be evaluated on a case-by-case basis upon consultation between the IND Office, Pfizer, and the principal investigator. At minimum, a review and discussion of potential delayed onset of significant toxicity will take place at each cohort review prior to a dose escalation decision.

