3.5 Dose Escalation and Stopping Rules

The decision to proceed to the next dose level will be made after the first three patients in a cohort have completed 56 days (2 cycles) of dosing (from Cycle 1 Day 1). Prior to advancing/changing dose levels, a cohort summary will be completed and submitted to the IND Medical Monitor for review and approval.

Dose de-escalation decisions will be made in accordance with a standard “3+3” study design using the rules below:

Table 7.

Number of Patients with DLT* at a Given Dose Level (assessed independent for each of arm)	De-Escalation Decision Rule
0 out of 3	Enter 3 more patients at this dose level
≥ 2	Dose de-escalation will occur. This dose level will be declared the maximally administered dose (highest dose administered). Three additional patients will be entered at the next lowest dose level.
1 out of 3	Enter at least 3 more patients at this dose level. If 0 of these 3 patients experience DLT, then this is the maximum tolerated dose (MTD). If 1 or more of this group suffer DLT, then dose de-escalation will occur. Three additional patients will be entered at the next lowest dose level.
MTD: The highest dose at which no more than 1 of 6 evaluable patients has had a DLT. Six patients should be treated before the dose is declared the MTD.	

Dose de-escalation will occur at the planned dose levels until the MTD is determined. The MTD is defined as the highest dose level with less than 2 patients with DLT out of at least six patients in the cohort. The recommended Phase 2 dose (RP2D) will be based on safety and preliminary efficacy data from the dose escalation and dose expansion cohorts.

All patients will be treated at the highest current dose level. All enrolled participants will be considered in the DLT analysis. If a DLT occurs in a cohort with 3 patients within first 56 days (from Cycle 1 Day 1), 3 additional patients will be enrolled in that cohort. If at any time more than or equal to one third (33%) of the participants at a dose level experience DLT, the MTD will be reassessed and the next lowest dose level for the combination therapy will be considered the MTD.

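### Section 3.3: on the nominal schedule the 28-day delay item is first met on Day 58, after the 56-day DLT window, and the replacement sentence removes patients held only for radiation toxicity

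*Combined protocol and SAP*

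**What the plan says.** Section 3.3 defines a DLT as "any of the following adverse events occurring in the first 56 days following Cycle 1 Day 1". Section 3.4 repeats the 56-day window for all arms. Two of the listed items concern treatment that stops or slips:

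- The item on stopping treatment reads "Discontinuation of a patient due a toxicity that is at least possibly study drug(s) and/or radiation related before completing DLT period".
- The item on late treatment, which is the subject here, reads "Delay by more than 4 weeks (28 days) in receiving the next scheduled cycle due to persisting toxicities attributable to the study drug(s) and/or radiation".

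For the Arm D de-escalation, 3.3 adds that "patients who missed any doses during the DLT period for reasons unrelated to study drug are not evaluable for DLT and will be replaced".

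Other sections bear on the same patients:

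- **3.5** makes the cohort decision once the first three patients have finished 56 days of dosing, which it equates with two cycles. It also says "All enrolled participants will be considered in the DLT analysis". A level is accepted with at most 1 DLT in 6 evaluable patients.
- **9.1** (per-protocol set) takes patients with a DLT in the 56 days or with the 56-day treatment completed without one.
- **5.2.3.2** defines a cycle as running from one Day 1 dose to the next, which is four weeks only if nothing is delayed.
- **5.2.4.2** caps a delay at 28 days, allows case-by-case exceptions, and holds avelumab or utomilumab for Grade 3-4 radiation diarrhea.
- **The synopsis** puts the window at two cycles or eight weeks and requires attribution to the study drugs, without mentioning radiation.

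**The concern.** A listed DLT criterion should be able to occur inside the window in which DLTs are counted. The 72-hour and 7-day items lose only events that begin in the last days of the window. The delay item is different: on the nominal schedule it falls outside the window however early the toxicity starts.

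The second problem does not depend on day counting. Section 3.3 treats study drug and radiation as separate causes and counts toxicity from either. Its replacement sentence exempts only drug-related reasons. A patient whose doses are held for radiation toxicity alone can therefore meet a DLT item and also be declared non-evaluable and replaced. Radiation is the only component de-escalated in Arm D (24 Gy to 21 Gy), and estimating that arm's MTD is a primary objective. The decision turns on 1 versus 2 DLTs in 6, so the scoring of a single patient can decide it.

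**Working it through.** **The plan's own figure.** Two cycles of 28 days give 2 x 28 = 56 days, as 3.5 states. The window's last day is Day 56 if Cycle 1 Day 1 is counted, or Day 57 if the 56 days begin after it.

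**When the delay item is first met.** A delay of more than 28 days is first true on the scheduled day + 29. Cycle 2 is nominally due on Day 1 + 28 = Day 29. The Arm D schedule allows +/-2 days.

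| Cycle 2 scheduled on | First day with delay over 28 days | In window ending Day 56 | In window ending Day 57 |
|---|---|---|---|
| Day 27 | Day 56 | yes | yes |
| Day 28 | Day 57 | no | yes |
| Day 29 (nominal) | Day 58 | no | no |
| Day 30 | Day 59 | no | no |
| Day 31 | Day 60 | no | no |

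The item fits for 1 or 2 of the 5 possible scheduled days. For Cycle 3, nominally due on Day 57, it is first met on Day 57 + 29 = Day 86.

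**Whether the discontinuation item covers the gap.** The 28-day cap in 5.2.4.2 falls on Day 29 + 28 = Day 57, so discontinuation at the cap is a DLT only if the window includes Day 57. Another sentence of 5.2.4.2 discontinues after more than four weeks, which is Day 58. Table 8 stops treatment for most drug-related Grade 3 reactions. It also stops treatment for Grade 2 reactions that recur or do not resolve; if one starts in Cycle 2, that point is the end of Cycle 3, nominally 3 x 28 = Day 84.

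**Who is left.**

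- Drug-related cytopenias that block re-treatment but meet no graded DLT item: afebrile ANC of 500-999, platelets below 50,000 without Grade 4 or bleeding, hemoglobin below 8 g/dL without Grade 4 anemia. This applies where the site follows the withholding text of 5.2.4.2 and not Table 8.
- Grade 2 toxicity held up to or past the Day 56-57 boundary.
- Patients allowed to continue case by case after more than 28 days.

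The utomilumab background (1.2.2) suggests the first group is uncommon. It reports one Grade 3 platelet decrease lasting under 7 days, given with rituximab.

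**Radiation-only hold.** Take Grade 3 diarrhea from radiation lasting 72 hours or more.

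- The diarrhea item in 3.3 makes it a DLT.
- 5.2.4.2 holds the drugs.
- The replacement sentence in 3.3, read literally, makes the patient non-evaluable.
- 9.1 includes the patient, as one with a DLT inside 56 days.
- The synopsis would not call it a DLT, because the cause is not a study drug.

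**What the scoring of one such patient does.** The documents give no DLT rate, so p = 10%, 20% and 30% are assumed for the other patients, independently. Acceptance of 24 Gy means at most 1 DLT in 6.

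| Scoring | Formula | p = 10% | p = 20% | p = 30% |
|---|---|---|---|---|
| DLT | P(Bin(5,p) = 0) | 59% | 33% | 17% |
| Replaced | P(Bin(6,p) <= 1) | 89% | 66% | 42% |
| Non-DLT | P(Bin(5,p) <= 1) | 92% | 74% | 53% |

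For the delay item the relevant contrast is DLT versus non-DLT, since 3.3 does not replace drug-related holds. For the radiation-only hold it is DLT versus replaced.

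**The case against.** The strongest reply is that the calendar gap is only a day or two and that other text closes it. Section 3.3 dates adverse events, and the adverse event is the toxicity, with the delay as its consequence. Dating by onset is a natural reading, but 3.3 lists the delay itself among the events and gives no onset rule. Even with onset dating, whether a delay will pass 28 days is unknown at Day 56.

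A reader might go further and infer that the status of any patient on hold at the cohort decision is left wholly open. The documents do not support that. Under 5.2.3.2 a patient whose Cycle 2 is held is still in Cycle 1 and so has not finished the two cycles that 3.5 asks for. On that reading the decision already waits. The synopsis window, read the same way, could stretch far enough to capture the delay. What stands is that waiting does not bring a Day 58 event inside the fixed 56-day window of 3.3 and 3.4, and that the synopsis and 3.3 can then give different answers.

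On the residual group, 5.2.4.3 requires drugs to be withheld according to Tables 8-10, and Table 8 discontinues Grade 3 reactions. Its laboratory exception covers only values unlikely to be related to treatment. That narrows the group, but 5.2.4.2 tells the site to withhold and resume for Grade 3 or higher laboratory abnormalities attributed to treatment, so it is not empty.

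On radiation, Appendix 1 reserves the unrelated category for events clearly due only to outside causes, and a plausible time sequence is enough for relatedness. Since drug treatment follows radiation within 3 days, few holds would be purely non-drug. This limits how often the conflict arises but does not remove it.

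Finally, 3.3 lets the PI decide that events which "do not meet the definition of a DLT but are concerning to the PI, may be then considered to be DLTs". Section 3.4 adds: "At minimum, a review and discussion of potential delayed onset of significant toxicity will take place at each cohort review". Section 3.5 requires medical monitor approval before dose levels change. These may well catch the patient, but by judgment and not by the written rule.

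**Conclusion.** Two sentences in 3.3 do not work as written for the Arm D de-escalation, and both are worth fixing. The delay item is first met on Day 58 for Cycle 2 or Day 86 for Cycle 3, after the window closes. This rests on the nominal schedule and on the literal dating of the delay; early scheduling of Cycle 2 or onset dating would change it. The replacement sentence conflicts with the radiation-related DLT items of the same section. This rests on study drug not including radiation, a distinction 3.3 itself draws.

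The affected group is small. A reader might infer from the acceptance probabilities that the design is biased toward accepting 24 Gy. That does not follow: the frequency of such patients cannot be derived, the PI may score them as DLTs, and the figures are conditional on such a patient existing and on assumed DLT rates. They show that the scoring matters, not how often it will.

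**What to change.** - **3.3, delay item:** count a delay of more than 28 days, or discontinuation for the same toxicity, as a DLT when the causing toxicity starts within 56 days of Cycle 1 Day 1.
- **3.3, replacement sentence:** limit replacement to doses missed for reasons related to neither study drug nor radiation.
- **Synopsis:** add radiation to the attribution rule and align the window with 3.3.
- **3.5 and 9.1:** state that a patient on a toxicity hold at Day 56 is pending, and that the cohort decision follows once the hold resolves.

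The length of delay that counts as dose-limiting remains the sponsor's choice.

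The cost is a few sentences and some waiting: about 58 - 56 = 2 days for a Cycle 2 hold, and up to about 86 - 56 = 30 days for a Cycle 3 hold. The wait arises only when a patient is on a toxicity hold at Day 56. Adding radiation to the replacement sentence delays nothing.

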3.4 Maximum Tolerated Dose (MTD) Definition

In the Dose De-Escalation cohorts, patients will be assigned sequentially into cohorts of up to six patients in each cohort. Three to six patients will initially be enrolled in each cohort for DLT observation. A total of six patients will be enrolled in a cohort in the event that a DLT is observed in one of the first three patients and/or additional safety data are needed.

The MTD is defined as the highest dose level with less than 2 patients with DLT out of at least six patients in the cohort. Management and dose modifications associated with adverse events are outlined in subsequent protocol sections.

For all Arms, the DLT assessment window is 56 days (from Cycle 1 Day 1). In the absence of DLTs, patients continue consecutive treatment. For patients who experience a DLT, they may continue treatment with modifications if the toxicity resolves and at discretion of the attending physician and PI. In the absence of clinical deterioration and if the investigator believes that the patient continues to receive benefit from the treatment, patients may continue to receive study drug combinations after the first indication of progressive disease until a confirmation scan is obtained.

To understand and safeguard against potential cumulative toxicities the study team will continue to monitor the occurrence of study drug related SAEs and AEs throughout the treatment period and during potential treatment extensions to allow for dose correction in the event of cumulative immune-mediated toxicities.

Delayed onset of significant toxicity at the discretion of the investigator will be evaluated on a case-by-case basis upon consultation between the IND Office, Pfizer, and the principal investigator. At minimum, a review and discussion of potential delayed onset of significant toxicity will take place at each cohort review prior to a dose escalation decision.

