For the objective of describing the toxicity profile, descriptive statistics will be provided on the grade and type of toxicity by dose level. Clinical efficacy will be measured by objective tumor response per RECIST criteria. The clinical response is defined as a CR or PR or at least 6 months SD. A 95% confidence interval of response rate will be estimated based on a binomial distribution.

Table 12: Total Planned Accrual for Each Treatment Arm

Treatment Arm	Dose Escalation	MTD Expansion	Total Enrollment
Arm A: Avelumab + Utomilumab (4-1BB)	NA (Escalation at Pfizer)	N=8 (Prior to Amendment Version 06)	24
		N=16 (As of Amendment Version 06)	
Arm B: Avelumab + PF-04518600 (OX40)	NA (Escalation at Pfizer)	N=12 (Prior to Amendment Version 06)	28
		N=14 (As of Amendment Version 06) *Treated 16 after replacing 2 patients with IND Office Approval	
Arm C: Avelumab + Utomilumab (4-1BB) + PF-04518600 (OX40)	N=4 NA (Escalation at Pfizer)	N=11 (Prior to Amendment Version 06)	32
		N=14 (As of Amendment Version 06) *Treated 17 after replacing 3 patients with IND Office Approval	
Arm D: Avelumab + Utomilumab (4-1BB) + XRT		N=4 (Prior to Amendment Version 08)	33
		N=3 (On Amendment 08)	

Treatment Arm	Dose Escalation	MTD Expansion	Total Enrollment
	N=12 (As of Amendment 09)		
Arm E: Avelumab + PF-04518600 (OX40) + XRT	N=3 (Prior to Amendment Version 08)	Closed per Amendment Version 09	6
	N=3 (On Amendment 08)		
Arm F: Avelumab + Utomilumab (4-1BB) + PF-04518600 (OX40) + XRT	N=4 (Prior to Amendment Version 08)	Closed per Amendment Version 09	7
	N=3 (On Amendment 08)		
Total	36	92	128

MDACC Investigational New Drug (IND) Office, Medical Affairs and Safety Group will review safety and efficacy data with Principal Investigator (and statistician if needed), at a predetermined interval as indicated next:

PHASE I

The first analysis will occur after the first 3 evaluable subjects per arm (Arm D), are treated for 56 days from Cycle 1 Day 1 and prior to advancing/changing dose levels; and every 3 evaluable subjects thereafter.

PHASE II

Efficacy/toxicity analysis will occur every 7 evaluable subjects per arm when treated for 6 months after the first study therapy dose. Assess toxicity at the end of the first 56 days following Cycle 1 Day 1, and response after 6 months of treatment. On every report submission, the information from previous reported patients will need to be updated for response.

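### Section 3.4 allows three to six patients to be enrolled initially at an Arm D dose level, which conflicts with the entry by threes in Section 3.5, Table 7 and Section 9.3

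*Combined protocol and SAP*

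**What the plan says.** Section 3.4 first says that "patients will be assigned sequentially into cohorts of up to six patients in each cohort", then that "Three to six patients will initially be enrolled in each cohort for DLT observation". Its next sentence reads "A total of six patients will be enrolled in a cohort in the event that a DLT is observed in one of the first three"; it also gives an alternative trigger, a need for more safety data.

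Section 3.5 names a standard 3+3 design and says "The decision to proceed to the next dose level will be made after the first three patients in a cohort have completed 56 days". Table 7 then acts on the result in three patients:

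- 0 of 3: "Enter 3 more patients at this dose level".
- 1 of 3: "Enter at least 3 more patients at this dose level".
- Two or more DLTs: de-escalate, and "Three additional patients will be entered at the next lowest dose level".

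Table 7 also requires six treated patients before a dose is declared the MTD.

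Section 9.3 sets the Phase I safety review in the same steps: "The first analysis will occur after the first 3 evaluable subjects per arm (Arm D), are treated for 56 days", and then after every further three evaluable patients. Section 3.1.1 uses three to six as the total per dose level, not the number that starts.

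Section 3.2.4 and Table 6 start Arm D at 24 Gy, with one lower level of 21 Gy. They record that the de-escalation was re-started under Amendment 09 because avelumab and radiation dosing had been revised.

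**The concern.** The two descriptions cannot both govern entry to a cohort. A site that follows Section 3.4 literally may enrol patients four, five and six before the first three have any 56-day result. A site that follows Table 7 would not, because there those patients enter as a consequence of 0 of 3 or 1 of 3.

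Section 3.4 is also inconsistent within itself and with Table 7. Having allowed up to six initially, it ties a total of six to a DLT in one of the first three or to a need for more safety data. Table 7 goes to six after 0 of 3 as well.

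The point matters more in Arm D than in an upward escalation. The first cohort is at the highest planned radiation level, so no lower cohort has screened for toxicity. Avelumab is first given on Cycle 1 Day 15, so the full combination cannot show toxicity in the first two weeks of the window. Quick accrual could therefore run ahead of the information that the three-patient step is meant to supply. DLTs and the MTD in Arm D are a primary objective.

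**Working it through.** **The plan's own figure.** Section 9.3 gives an Arm D de-escalation maximum of 2 levels × 6 patients = 12, which reproduces. The escalation column of Table 12 also sums as stated: 4 + 4 + 3 + 12 + 3 + 3 + 4 + 3 = 36. Neither figure depends on which entry rule is followed.

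**Two readings at one dose level.**

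- Staged (Table 7): treat three. If two or more have a DLT, de-escalate; otherwise treat three more. The calculation uses exactly three more after 1 of 3, although the table says at least three.
- Six initially (Section 3.4 read literally, worst case): all six are dosed before any DLT is known.

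**Input that is not in the documents.** The true DLT probability p is an assumption. The range 10% to 60% is shown.

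**Formulas**, with q = 1 − p:

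- Chance that the first three alone trigger de-escalation: S = 3p²q + p³.
- Expected patients treated, staged: 6 − 3S, against 6.
- Expected extra DLTs if six are dosed initially: 3 × p × S. This averages over all outcomes. In the triggering cases alone, the mean is 3p.
- Chance that the level qualifies (at most 1 of 6 with DLT), six initially: q⁶ + 6pq⁵.
- The same chance, staged: q³(q³ + 3pq²) + 3pq² × q³ = q⁶ + 6pq⁵.

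Example at p = 0.33: S = 3 × 0.1089 × 0.67 + 0.0359 = 0.255. Expected patients = 6 − 3 × 0.255 = 5.24. Extra DLTs = 3 × 0.33 × 0.255 = 0.25.

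| Assumed p | S | Expected patients, staged (vs 6) | Expected DLTs, staged vs six | Extra DLTs, overall | Extra DLTs when triggered (3p) | Level qualifies, both readings |
|---|---|---|---|---|---|---|
| 0.10 | 0.028 | 5.92 | 0.59 vs 0.60 | 0.01 | 0.30 | 0.886 |
| 0.20 | 0.104 | 5.69 | 1.14 vs 1.20 | 0.06 | 0.60 | 0.655 |
| 0.33 | 0.255 | 5.24 | 1.73 vs 1.98 | 0.25 | 0.99 | 0.358 |
| 0.50 | 0.500 | 4.50 | 2.25 vs 3.00 | 0.75 | 1.50 | 0.109 |
| 0.60 | 0.648 | 4.06 | 2.43 vs 3.60 | 1.17 | 1.80 | 0.041 |

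The last column is identical under the two readings, as the algebra shows. The entry rule changes how many patients are treated at a level that fails, not whether it fails.

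**The case against.** The strongest reply is that one loose sentence in a definitions section cannot override the operative rule. Much of this stands:

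- A reader might infer that six patients start simultaneously. The text does not say so. Section 3.4 speaks of sequential assignment and of the first three patients, and Section 5.1 has patients assigned successively with regard to those already enrolled. However, neither section states a hold after the third patient, and Section 5.1 ties the dose level to the previous cohort's evaluation.
- A reader might infer that nothing makes patients four to six wait. Table 7 does imply it, since their entry follows from 0 of 3 or 1 of 3, and Section 3.5 refers to adding three patients to a cohort of three. What is missing is an explicit enrolment hold; Section 3.5 attaches the 56-day point to moving to the next dose level.
- A reader might infer that the interim decision disappears. It does not. The row of Table 7 for two or more DLTs has no denominator, and Section 3.5 has a further rule that acts whenever a third or more of the participants at a level have a DLT. These rules could stop a cohort early, which is why the figures above are a worst case. They cannot undo doses already given.
- A reader might call the starting level untested. Section 9.3 records 7 earlier Arm D patients (4 + 3) on previous schedules, and Arm A uses the same listed utomilumab and avelumab doses without radiation. Only the current combination is new.

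**Conclusion.** The inconsistency is real and concerns the safety rule of the only arm still seeking an MTD. Section 3.4 permits, but does not plan, up to six patients at a level before a 56-day result. Table 7, Section 3.5 and Section 9.3 stage entry by threes.

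The consequence is avoidable exposure. It is negligible if the level is well tolerated (about 0.01 extra DLTs at an assumed 10%) and grows with toxicity (0.25 at 33%, 1.17 at 60%). These sizes rest on assumed DLT rates and on all six being dosed before any DLT is known. A reader might go on to infer that the MTD would be biased; the calculation does not support that, since the probability that a level qualifies is the same either way. The point merits a wording amendment, not a redesign.

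**What to change.** Reconcile Section 3.4 with Table 7 and Sections 3.5 and 9.3:

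1. Replace the sentence on initial enrolment of three to six with wording that matches Table 7's staged entry, and keep three to six as the total per level, as in Section 3.1.1.
2. State explicitly whether patients four to six wait for the 56-day result of the first three. If sign-off is also wanted before they enter, say so: Section 3.5 requires approval of the cohort summary before dose levels change, not before patients are added at the same level.
3. Rewrite the sentence on a total of six so that it covers both the 0 of 3 and 1 of 3 rows. Deleting only the clause on additional safety data would leave six tied to a DLT among the first three, and so create a new conflict with the 0 of 3 row.

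The cost is a short text amendment. Maximum accrual stays at 6 per level and 12 in all. The downside is a possible pause of up to 56 days per level, which Table 7 and the review after every three patients already imply.
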